### **8.6.3 Stopping Rules for Platelet Count Results**

Actions to be taken in the event of a low platelet count are summarized in [Table 4](#) below.

In the event of a platelet count less than  $75,000/\text{mm}^3$  that is associated with major bleeding or clinically-relevant non-major bleeding (defined below; [Schulman et al. 2005](#)), dosing of a patient with Study Drug will be stopped permanently. The follow-up schedule for any events meeting this stopping criterion will be determined by the Investigator in consultation with the Sponsor Medical Monitor.

In the event of any platelet count less than  $50,000/\text{mm}^3$ , or a platelet count less than  $75,000/\text{mm}^3$  that occurs while the patient is on dosing at 300 mg every 2 weeks then dosing of a patient with volanesorsen will be stopped permanently. Platelet count will be monitored as outlined in [Table 4](#).

Administration of corticosteroids is recommended for patients whose platelet count is less than  $50,000/\text{mm}^3$ . Recovery in platelet count may be accelerated by administration of high dose corticosteroids. Treatment guidelines for immune thrombocytopenia ([Provan et al. 2010](#)) recommend dexamethasone 40 mg daily for 4 days every 2-4 wk for 1-4 cycles; prednisolone 0.5-2 mg/kg/day for 2-4 weeks then taper; or methylprednisolone 30 mg/kg/day for 7 days (**note:** may require continuation with oral corticosteroids after methylprednisolone).

Triglyceride levels will be monitored weekly, and AE monitoring will continue during corticosteroid treatment and the laboratory alert will be changed from an increase of 2,000 to 500 mg/dL during that period.

In the event of a platelet count less than  $75,000/\text{mm}^3$ , and in the absence of major bleeding or clinically-relevant non-major bleeding (defined below; [Schulman et al. 2005](#)), dosing of a patient with Study Drug will be suspended temporarily until the platelet count has recovered to  $\geq 100,000/\text{mm}^3$ . If dosing is reinitiated it should be at a reduced dose frequency of 300 mg every 2 weeks (refer to [Section 8.7](#)). The suitability of the patient for reinitiation of dosing will be determined by the Investigator in consultation with the Study Medical Monitor and will be based on factors such as the original rate of decline in the patient's platelet count, whether any bleeding events were experienced by the patient, and the speed of recovery of platelet count upon holding of dosing.

If after the first dosing rechallenge the platelet count again falls below 75,000/mm^3, then dosing of the patient with Study Drug will be stopped permanently.

**Definition of Major Bleeding Events (Schulman et al. 2005):**

1. Fatal bleeding, and/or
2. Symptomatic bleeding in a critical area or organ, such as intracranial, intraspinal, intraocular, retroperitoneal, intra-arterial or pericardial, or intramuscular with compartment syndrome, and/or
3. Bleeding causing a fall in hemoglobin level of 20.0 g/L (1.24 mmol/L) or more within 24 hours, or leading to transfusion of 2 or more units of whole or red cells

**Definition of Clinically-Relevant, Non-Major Bleeding Events (Schulman et al. 2005):**

1. Multiple-source bleeding
2. Spontaneous hematoma > 25 cm^2
3. Excessive wound hematoma (not injection site related)
4. Macroscopic hematuria (spontaneous or lasting > 24 hours if associated with an intervention)
5. Spontaneous rectal bleeding; epistaxis, gingival bleeding, hemoptysis, hematemesis
6. Bleeding after venipuncture for > 5 minutes

**Table 4 Actions in Patients with Low Platelet Count or Drop in Platelet Count**

Platelet Count on Rx	Drug Dose	Monitoring
	Study Drug administration is contingent on the availability of the immediately preceding test result. An interpretable platelet value must be available within 7 days prior to dosing. Only the study doctor or qualified designee can authorize continued Study Drug administration based on an acceptable platelet value. Patients should not administer a dose until they have been contacted by their study doctor or designee and told that it is acceptable to dose. Authorization to dose must be documented in the patient's medical records.	Monitor every 1 week unless otherwise specified Obtain additional lab tests (Table 3) if 2 occurrences (consecutive or non-consecutive) of platelet count 140K - > 100K/mm  or 1 occurrence of platelet count ≤ 100K/mm  . Labs only need to be performed once. Labs may be collected over multiple visits, if blood requirements are a concern, as per Investigator discretion.
> 100K/mm 	Weekly 300 mg Study Drug administration	

**Table 4 Actions in Patients with Low Platelet Count or Drop in Platelet Count**  
*Continued*

Platelet Count on Rx	Drug Dose	Monitoring
100K/mm  - > 75K/mm 	Permanently reduce dose frequency to 300 mg every 2 weeks	
75K/mm  - > 50K/mm 	If occurs while on dose of 300 mg every 2 weeks then permanently discontinue Study Drug, otherwise dose pause When platelet count returns to > 100K/mm  restart dosing at dose frequency of 300 mg every 2 weeks only if approved by Sponsor Medical Monitor	Monitor every 2-3 days until 2 successive values are > 75K/mm  then monitor every 1 week Consider discontinuation of antiplatelet agents/NSAIDS/ anticoagulant medication
≤ 50K/mm 	
 
• Permanently discontinue Study Drug
 
	
 
• Monitor daily until 2 successive values show improvement then monitor every 2-3 days until 2 successive values are > 75K/mm^3 then monitor every 1 week
 
• Patient should be evaluated by a hematologist to provide diagnostic and therapeutic management
 
• Steroids recommended*. It is strongly recommended that, unless the patient has a medical contraindication to receiving glucocorticoids, the patient receives glucocorticoid therapy to reverse the platelet decline.
 
• Monitor triglyceride levels weekly and continue AE monitoring during steroid therapy
 
• Discontinue antiplatelet agents/NSAIDS/ anticoagulant medication while platelet count is < 50K/mm^3 if possible
 

\*\* Recovery in platelet count may be accelerated by administration of high dose corticosteroids. Treatment guidelines for immune thrombocytopenia ([Provan et al. 2010](#)) recommend dexamethasone 40 mg daily for 4 days every 2-4 wk for 1-4 cycles; prednisolone 0.5-2 mg/kg/day for 2-4 weeks then taper; or methylprednisolone 30 mg/kg/day for 7 days (**note:** may require continuation with oral corticosteroids after methylprednisolone)

#### **8.6.4 Stopping Rule for Documented Severe Hypoglycemia**

In the event of a first instance of documented severe hypoglycemia, dosing of a patient with Study Drug will be suspended temporarily. The need to adjust the background medication and the suitability of the patient for continued dosing will be determined by the Investigator in consultation with the Study Medical Monitor. In the event of a second instance of documented severe hypoglycemia, after a rechallenge, dosing of a patient with Study Drug will be stopped permanently.

#### **8.7 Adjustment of Dose and/or Treatment Schedule**

Dose adjustments for platelet count reduction must be made in accordance with [Section 8.6.3](#) and [Table 4](#) above.

Other dose adjustments, including dose interruptions, and/or decreasing the dose or dose frequency will be allowed for safety and tolerability. Any proposed adjustment to treatment schedule must be discussed with, and approved by, the Study Medical Monitor prior to initiation. Dose adjustments should not occur unless absolutely necessary prior to the primary analysis time point (Month 3).

Patients may be dose paused in response to AEs after consultation with Study Medical Monitor.

## **8.8 Discontinuation of Study Treatment**

A patient must permanently discontinue study treatment for any of the following:

- The patient becomes pregnant. Report the pregnancy according to instructions in [Section 9.5.4](#)
- The patient withdraws consent
- The patient experiences an AE that necessitates permanent discontinuation of study treatment
- The patient develops laboratory test abnormalities that meet any of the stopping rules listed in [Section 8.6](#)
- The patient experiences an AE that necessitates unblinding of the Investigator to the patient's treatment assignment

The reason for discontinuation of study treatment must be recorded in the electronic Case Report Form (eCRF) and source documentation.

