## **8.5 Safety Monitoring Rules**

In addition to the standard monitoring of clinical safety parameters, the following guidelines are provided for the monitoring of selected parameters chosen based on preclinical and clinical observations.

Please refer also to the 'Guidance for Investigator' section of the Investigator's Brochure.

For the purposes of safety monitoring baseline is defined as the average of Day 1 pre-dose assessment and the last measurement prior to Day 1.

**Confirmation Guidance:** At any time during the Study (Randomized Treatment, OLE, or Post-Treatment Periods), the initial clinical laboratory results meeting the safety monitoring criteria presented below **must be confirmed** by performing measurements (ideally in the same laboratory that performed the initial measurement) on new specimens. All new specimen collections should take place as soon as possible (ideally within 3 days of the initial collection). For stopping rules, if the initial laboratory result is observed during the Treatment Period, the results from the retest **must be available** prior to administering the next dose of Study Drug.

**Re-dosing Guidance:** Patients with initial laboratory test values that reach a stopping rule must not be re-dosed until the re-test results are available. In general, patients who do not meet the stopping rules based upon retest may continue dosing. However, the Investigator and the Sponsor Medical Monitor (or appropriately qualified designee) should confer as to whether additional close monitoring of the patient is appropriate. Reduction in dose or dose frequency may also be initiated as noted in [Section 8.7](#). If any of the stopping criteria described below are met below (refer to [Sections 8.6.1](#) to [8.6.3](#)) and are confirmed, the patient will be dose paused or permanently discontinued (as described in the appropriate stopping criterion) from further treatment with Study Drug, and evaluated fully as outlined below and in consultation with the Sponsor Medical Monitor or appropriately qualified designee, and will be entered into the post-treatment evaluation portion of the study (see [Section 8.8](#)).

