### **8.6.1      *Stopping Rules for Liver Chemistry Elevations***

In the event of confirmed laboratory results meeting the following criteria, **and the event is without an alternative explanation as discussed with the Sponsor Medical Monitor**, dosing of a patient with Study Drug will be stopped permanently:

1. ALT or AST  $> 8 \times$  ULN, which is confirmed
2. ALT or AST  $> 5 \times$  ULN, which is confirmed and persists for  $\geq 2$  weeks
3. ALT or AST  $> 3 \times$  ULN (or the greater of 2 x Baseline value or 3 x ULN if the Baseline value was  $>$  ULN), which is confirmed **and** total bilirubin  $> 2 \times$  ULN or INR  $> 1.5$
4. ALT or AST  $> 3 \times$  ULN (or the greater of 2 x Baseline value or 3 x ULN if the Baseline value was  $>$  ULN), which is confirmed, and the new appearance (i.e., onset coincides with the changes in hepatic enzymes) of fatigue, nausea, vomiting, right upper quadrant pain or tenderness, fever, rash, or eosinophilia ( $>$  ULN) felt by the Investigator to be potentially related to hepatic inflammation

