### **8.6.2 Stopping Rules for Renal Function Test Results**

In the event of persistent changes that are observed over 2 consecutive weeks, for any of the criteria below, dosing of a patient with Study Drug may be stopped temporarily:

1. Quantitative total urine protein measurement of  $> 3.5$  g/24 hours
2. Estimated creatinine clearance calculated according to the formula of Cockcroft and Gault  $\leq 40$  mL/min that is confirmed by a 24-hour urine collection

The possible dosing re-initiation or follow-up schedule for any events meeting either of these criteria will be determined by the Investigator **in consultation with** the Sponsor Medical Monitor or designee.

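### Protocol 8.8 requires permanent discontinuation for laboratory events that the platelet pause in 8.6.3 and the renal rule in 8.6.2 treat as temporary holds, and no other section settles which applies

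*Protocol*

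**What the plan says.** Protocol 8.8 opens its list with "A patient must permanently discontinue study treatment for any of the following", and one item is "The patient develops laboratory test abnormalities that meet any of the stopping rules listed in" Section 8.6. No rule within 8.6 is exempted.

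Section 8.6 contains four sets of rules:

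- **8.6.1 (liver):** "dosing of a patient with Study Drug will be stopped permanently".
- **8.6.2 (renal):** "dosing of a patient with Study Drug may be stopped temporarily", followed by "The possible dosing re-initiation or follow-up schedule for any events meeting either of these criteria will be determined by the Investigator" in consultation with the medical monitor.
- **8.6.3 (platelets):** below 75,000/mm3 without major or clinically relevant non-major bleeding, "dosing of a patient with Study Drug will be suspended temporarily until the platelet count has recovered to" 100,000/mm3 or more, with any restart at reduced frequency. Table 4 calls this a dose pause and makes restart depend on the medical monitor's approval. The stop is permanent below 50,000/mm3, with qualifying bleeding, when the fall occurs on every-2-week dosing, or when the count falls again after a rechallenge.
- **8.6.4 (documented severe hypoglycaemia):** at the first instance "dosing of a patient with Study Drug will be suspended temporarily"; at a second, after rechallenge, the stop is permanent.

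The re-dosing guidance in 8.5 covers 8.6.1 to 8.6.3. It says that a patient with a confirmed criterion is either paused or permanently discontinued, as that criterion describes. The same sentence adds that the patient "will be entered into the post-treatment evaluation portion of the study", with a pointer to 8.8.

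**The concern.** An investigator with a platelet count in the pause range has two instructions. 8.6.3 says to suspend and consider restarting; 8.8 says treatment must end. Both are written as requirements. In the renal case one section allows a temporary stop and the other requires a permanent one.

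Two things are at stake. The first is consistent handling: sites may treat the same laboratory result differently, and either choice can be read as a deviation. SAP Appendix A lists, among the deviation types reported to the DSMB, failure to withdraw a patient as the protocol requires and failure to comply with stopping rules. The second is the data. The pause-or-stop classification feeds disposition, exposure and the stopping-rule listing in SAP 3.7.4. Through the on-treatment window in SAP 3.2.1, it can also decide which efficacy values are used.

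**Working it through.** The plan gives no figure to reproduce. The check is a rule-by-rule comparison, followed by the arithmetic of the on-treatment window.

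**Step 1. Each 8.6 rule against 8.8 (permanent stop, compulsory).**

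| Rule | Outcome in 8.6 | Against 8.8 |
|---|---|---|
| 8.6.1 liver | permanent | agrees |
| 8.6.2 renal | temporary, permitted (*may*) | conflicts: compulsory permanent against permitted temporary |
| 8.6.3 and Table 4, pause tier on weekly dosing | temporary, required (*will*) | direct contradiction |
| 8.6.3 and Table 4, permanent tiers | permanent | agrees |
| 8.6.4 first event | temporary, required | arguable |
| 8.6.4 second event after rechallenge | permanent | agrees |

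The 8.6.4 first event is arguable because the 8.8 item concerns laboratory test abnormalities. Section 8.5.7 defines documented severe hypoglycaemia as an event needing another person's help together with a glucose value. 8.5 cites only 8.6.1 to 8.6.3, and SAP 3.7.4 names only liver, renal and platelet categories.

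**Step 2. Do other sections resolve it?** 8.5 defers to the specific criterion, 8.7 ties platelet dose adjustments to 8.6.3 and Table 4, and 6.2.2 names a dose pause rule at 75,000/mm3 separately from a stopping rule. These point one way. But 8.6.3 puts the pause under a stopping-rules heading, 8.8 refers to all of 8.6, and 8.5 itself counts a pause among the outcomes of a stopping criterion. 8.5 then routes patients to post-treatment evaluation without separating those who are only paused.

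**Step 3. Effect on the Month 3 value.** Inputs: on-treatment means up to last dose + 28 days (SAP 3.2.1); the Week 12 lipid window is Days 65 to 82 and Week 13 is Days 83 to 106 (SAP Appendix B), with target Days 78 and 85; one of the two visits is enough (SAP 3.2.3); patients with no value are excluded from the primary analysis (SAP 3.3.2, 3.3.5).

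- Last dose on Day 36: 36 + 28 = Day 64, before the window opens on Day 65. No Month 3 value can count.
- Last dose on Day 50: 50 + 28 = Day 78. The Week 12 visit on its target day counts.
- Last dose on Day 57: 57 + 28 = Day 85. Both target visits count.
- Last dose between Days 37 and 49: a value counts only if a sample happens to fall between Day 65 and last dose + 28.

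For a patient who is paused and restarted, the last dose is the later one, so values taken during the pause stay inside the window. A patient paused and never restarted has the same last dose as one stopped permanently. The classification therefore changes the Month 3 data only for early events followed by a restart. Membership of the full analysis set does not change.

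**Step 4. The SAP listing.** SAP 3.7.4 lists patients who terminated treatment under an 8.6 rule and includes a renal category, yet 8.6.2 on its own terms names no permanent stop. Who belongs in that category depends on whether 8.6.2 or 8.8 is followed.

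**The case against.** The strongest reply is that a site reading the whole of Section 8 gets a workable platelet instruction. 8.5 lets the specific criterion choose between pause and stop, 8.7 makes 8.6.3 and Table 4 binding for platelet adjustments, Table 4 separates a pause from permanent discontinuation, and 6.2.2 and the schedule footnotes keep the pause rule apart from stopping rules. On that usage 8.8 need not reach the pause at all. This stands as evidence of intent. It does not change the wording of 8.8, and it leaves the closing clause of 8.5 unexplained.

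Some stronger readings are tempting but unsupported:

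- **That three of the four rule sets carry opposite mandatory outcomes.** Only the platelet pause tier does. The renal rule is permissive, the hypoglycaemia rule may lie outside the 8.8 item, and restart is conditional throughout.
- **That 6 of 182 patients (3.3%), from Protocol 2.3.4, measures the problem.** Those were other, blinded trials, and the count covers any interruption or stop. Two of the six had counts below 25,000/mm3, a permanent stop under both sections here. At most 6 − 2 = 4 of 182 (2.2%) could fall in the disputed tier, and their counts are not given.
- **That the conflict falls mainly on the active arm.** The six cases are not given by arm. A mild Phase 2 platelet decrease associated with the drug makes the inference plausible but does not establish it.
- **That the primary analysis is broadly affected.** Only early events can matter, and only when dosing restarts.

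**Conclusion.** The inconsistency is real and should be corrected. It is an internal contradiction in the protocol, not a design choice. It is direct for the 8.6.3 and Table 4 pause tier, present in weaker form for 8.6.2, and arguable for the first event in 8.6.4. The liver rule, the permanent platelet tiers and the second hypoglycaemia event agree with 8.8.

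The certain effect is on handling, disposition and the SAP listing. The effect on the Month 3 endpoint is conditional: it needs a last dose before the event at Day 36 or earlier (possibly as late as Day 49), and a restart under one reading that the other forbids. With the sample size reasoning based on 20 patients per arm, each such patient would be 1/20 = 5% of an arm. The documents give no basis for saying how many there would be. These statements assume the SAP's last dose means the final dose after any restart, and that visits fall on their target days where stated.

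**What to change.** Reconcile Protocol 8.5, 8.6.2, 8.6.3 with Table 4, 8.6.4 and 8.8 so that each 8.6 rule has one stated outcome and 8.5 and 8.8 repeat it. State whether the 8.8 item covers 8.6.4. Make clear which patients enter post-treatment evaluation, and in particular whether a paused patient does. Use the terms pause rule and stopping rule in the same way in 6.2.2, the schedule footnotes and 8.6.3. Which outcome applies to each rule is for the clinical team.

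In the SAP, define which of these patients count as having terminated treatment for the 3.7.4 listing, including the renal category, and align disposition with that definition.

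The cost is a short protocol clarification and a sentence or two in the SAP, with no change to assessments or sample size. SAP 3.1 and 3.8 record that study treatment ended before the planned period was complete, but disposition and the listing still need a single definition.

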### ***8.8.1 Follow-up Visits for Early Termination from Treatment and OLE Periods***

Patients should be strongly encouraged to attend applicable landmark visits at Weeks 12, 13, 25, 26 and 50, 52 of Randomized Treatment period (calculated based on the time elapsed since Day 1) and at Weeks 64, 65, 77, 78 and 102, 104 of OLE period to collect fasting lipid panels and conduct safety assessments in accordance with the schedule of procedures in [Appendix A](#).

Any patient who discontinues early from treatment in the Randomized Treatment Period or OLE with platelet counts < LLN should be followed as per [Section 8.5.3](#) (Safety Monitoring for Platelet Count Results) and [Section 8.6.3](#) (Stopping Rules for Platelet Count Results) for the first 6 weeks after discontinuing Study Drug. Following this period, if the platelet count is stable (at least 3 consecutive values that are stable as determined by the Sponsor Medical Monitor and  $> 100,000/\text{mm}^3$ ), the next platelet count should be taken within at least 6 weeks so that patients are monitored for at least 12 weeks after discontinuing Study Drug.

If the patient declines or is unable to participate in the above, an early termination visit (Week 52 or Week 104 visit assessments) should be performed at the time of withdrawal, at a minimum, and ideally within 2 weeks from the last dose of Study Drug.

### ***8.8.2 Follow-up Visits for Early Termination from Post-Treatment Follow-up Period***

Patients should be encouraged to undergo a final follow-up visit (Week 117 for OLE for post-treatment follow-up, see [Appendix A](#)) prior to leaving the study.

The patient who requests to withdraw from the study during the Post-Treatment Follow-up Period with platelet counts < LLN should also be encouraged to follow the platelet monitoring rules as per [Section 8.5.3](#) (Safety Monitoring for Platelet Count Results) and [Section 8.6.3](#) (Stopping Rules for Platelet Count Results) for the first 6 weeks after discontinuing Study Drug. Following this period, if the platelet count is stable (at least 3 consecutive values that are stable as determined by the Sponsor Medical Monitor and > 100,000/mm^3), the next platelet count should be taken within at least 6 weeks so that patients are monitored for at least 12 weeks after discontinuing Study Drug.

If a patient withdraws due to an AE at any time during the study, the Investigator should arrange for the patient to have appropriate follow-up until the AE has resolved or stabilized.

